| Baseline information on IPF First symptoms; date of first diagnosis; if performed, dates and results of HRCT, surgical lung biopsy, bronchoalveolar lavage. | X | | | | |
| IPF Symptoms Cough, Fatigue, Dizziness, Chest pain, Clubbing, Bibasilar crackles. | X | X | X | X | X |
| Functional assessment Lung function test (VC, FVC, FVC % predicted, FEV1, TLC, DLCO, DLCO % predicted, pO2, pCO2; SaO2, PaO2 and PaCO2 at rest); 6-minute walk distance (if performed) | X | X | X | X | X |
| Exacerbations Onset and end date Description of management (if available) | X | X | X | X | X |
| Pharmacological treatments related to both IPF and adverse events (drug, dosage regimen, start / end date or ongoing): Steroids, anticoagulants, immunomodulators (azathioprine, cyclophosphamide, MMF, etc), N- | X | X | X | X | X |

| Study Visits | Visit 1 | Visit 2 | Visit 3 | Visit 4 | Visit 5 |
|--|----------|-------------|-------------|-------------|-------------|
| | Baseline | Follow-up 1 | Follow-up 2 | Follow-up 3 | Follow-up 4 |
| Months | 0 | 3 (+/- 1) | 6 (+/- 1) | 9 (+/- 1) | 12 (+/- 1) |
| Acetylcysteine, Pirfenidone, Nintedanib | | | | | |
| Presence on listing for lung transplantation (yes/no) | X | X | X | X | X |
| Non Pharmacological treatment - Pulmonary rehabilitation; - Long-Term Oxygen Therapy (liquid and/or concentrate). | X | X | X | X | X |
| Health-care resource consumption related to both IPF and IPF-related adverse events: hospitalization (inward and day-hospital), emergency room access, specialist visits, General Practitioner visits, laboratory tests or examinations, imaging sessions, pharmacological and non-pharmacological treatments | X | X | X | X | X |
| Patient Reported Outcomes Questionnaires/scales | | | | | |
| HRQoL EQ-5D-5L descriptive system and EQ VAS; Saint George Respiratory Questionnaire (SGRQ) | X | | X | | X |
| | | | | | |
| | | | | | |
| | | | | | |
| Survival Status | | X | X | X | X |
| Adverse Events and Adverse Drug Reactions description, onset and resolution date, relation with drugs, severity, seriousness. | | X | X | X | X |
| Clinical events CNS infarction; myocardial infarction; other arterial thromboembolic events; deep vein thrombosis; hemorrhage; gastrointestinal perforation; pulmonary hypertension) | | X | X | X | X |

Visit 2 (3+/-1 month), Visit 3 (6+/-1 month) and Visit 4 (9+/-1 month) are referred as being the current clinical practice in Italy for IPF patients management.

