10.2 ADVERSE EVENT AND SERIOUS ADVERSE EVENT COLLECTION AND REPORTING

The investigator shall maintain and keep detailed records of all AEs in their patient files.

Collection of AEs

The study design is of non-interventional nature and the study is conducted within the conditions of the approved marketing authorization. Sufficient data from controlled interventional trials are available to support the evidence on the safety and efficacy of the studied BITSPA drug. For this reason the following AE collection and reporting requirements have been defined.

The following must be collected by the investigator in the (e)CRF from signing the informed consent onwards until the end of the study for the BITSPA product administered for the disease in scope of the study:

- all ADRs (serious and non-serious),
- all AEs with fatal outcome ,
- all pregnancies

All ADRs , including those persisting after study completion must be followed up until they are resolved, have been sufficiently characterized, or no further information can be obtained.

The investigator carefully assesses whether an AE constitutes an ADR using the information below.

Causal relationship of adverse event

The definition of an adverse reaction implies at least a reasonable possibility of a causal relationship between a suspected medicinal product and an adverse event. An adverse reaction, in contrast to an adverse event, is characterized by the fact that a causal relationship between a medicinal product and an occurrence is suspected.

Medical judgment should be used to determine the relationship, considering all relevant factors, including pattern of reaction, temporal relationship, de-challenge or re-challenge, confounding factors such as concomitant medication, concomitant diseases and relevant history.

Arguments that may suggest a reasonable causal relationship could be:

- The event is consistent with the known pharmacology of the drug

- The event is known to be caused by or **attributed to the drug class**.
- A **plausible time to onset of the event** relative to the time of drug exposure.
- Evidence that the **event is reproducible** when the drug is re-introduced
- **No medically sound alternative etiologies** that could explain the event (e.g. preexisting or concomitant diseases, or co-medications).
- The event is typically **drug-related and infrequent in the general population** not exposed to drugs (e.g. Stevens-Johnson syndrome).

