At each follow-up visit all treatments having (start date **[F24_NON_PHARMACOLOGICAL_THERAPY.START_DATE_NF]** >= date of first IPF diagnosis (mm/yyyy) **[F05_DIAGNOSIS_IPF.DIA_Date_IPF_diagnosis]** AND < date of follow-up visit) AND ((end date **[F24_NON_PHARMACOLOGICAL_THERAPY.END_DATE_NF]** >= date of first IPF diagnosis (mm/yyyy) **[F05_DIAGNOSIS_IPF.DIA_Date_IPF_diagnosis]** AND end date > date of follow-up visit **[F16_PATIENT_DISPOSITION.PD_2]**) OR (end date = missing and "Ongoing at the end of observation?" = "Yes") **[F24_NON_PHARMACOLOGICAL_THERAPY.ONGOING_NF_THER]**) will be selected.

Patients with AEs or ADRs during observation period

Are defined as patients with at least one AEs or ADRs between diagnosis and end of observation defined as events with date of diagnosis <= start date AE <= date of last available follow up.

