4.14 AEs and ADRs between diagnosis and end of observation**Table 52. Patients with AEs and ADRs between diagnosis and end of observation**

The table will provide the absolute and relative frequency of the patients with at least one adverse events between diagnosis and end of observation.

The total number of evaluable patients at enrollment will be considered.

Listing 53. AEs and ADRs between diagnosis and end of observation

The table will provide the distribution of every AE or ADR, occurred between diagnosis and end of observation by serious AE, seriousness category and causal relationship with Nintedanib.

The total number of evaluable patients at enrollment will be considered.

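### SAP Table 52 and Listing 53 name an adverse-event window that opens at IPF diagnosis, but the protocol plans no AE collection before informed consent

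*SAP*

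**What the plan says.** **SAP.** Section 3 defines patients with AEs or ADRs during the observation period through "events with date of diagnosis <= start date AE <= date of last available follow up". In section 4.14, Table 52 reports "patients with at least one adverse events between diagnosis and end of observation" and Listing 53 gives the "distribution of every AE or ADR, occurred between diagnosis and end of observation", including the causal relationship with nintedanib. For both outputs, "The total number of evaluable patients at enrollment will be considered".

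**Protocol.** Section 10.2 lists what the investigator must collect "in the (e)CRF from signing the informed consent onwards until the end of the study": all ADRs, AEs with fatal outcome, and pregnancies, for the sponsor's product given for IPF. The expedited-reporting rules in the same section use the same start and end. In the section 8.3 schedule the AE/ADR row reads "description, onset and resolution date, relation with drugs, severity, seriousness. | | X | X | X | X"; the empty first cell is Visit 1. Inclusion criterion 3 (section 8.2) admits a diagnosis made within the previous 3 months. Section 8.7 does plan retrospective collection or estimation for the time between diagnosis and inclusion, but for health care resources only.

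**The concern.** The analysis window and the collection window start at different dates, and no section of either document bridges the interval for adverse events. A reader of Table 52 would take its percentage as the frequency of AEs/ADRs from diagnosis onwards, although the design did not observe the first part of that period.

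The interval is not empty of exposure by construction. The SAP rule for treatments ongoing at enrollment selects drugs started on or after diagnosis and before the enrollment visit, and Table 43 reports the time from diagnosis to first therapy. For a patient who starts the sponsor's product before consent, the first weeks on drug fall inside the named window and outside planned collection. If a site does enter such an event, the SAP filter counts it. Early events would then enter according to site habit, not by a rule.

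**Working it through.** The documents state no AE frequency or rate, so there is no plan figure to reproduce. The check compares the two windows.

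**1. Inputs**
- Counting window: diagnosis to last available follow-up (SAP section 3).
- Collection window: consent to end of study (protocol 10.2), with no AE entry at Visit 1 (protocol 8.3).
- Gap g: nominally 0 to 3 months (protocol 8.2, inclusion criterion 3).
- Follow-up: 12 months (protocol 8.1).
- Planned enrollment: 200 (SAP section 1).

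**2. What the SAP filter does.** Let N be the patients evaluable at enrollment, R the patients with at least one recorded event in the SAP window, and M the patients whose only event began before consent and was not recorded.
- Reported percentage = R/N.
- True percentage for the named window = (R + M)/N.
- Shortfall = M/N, which is never negative.

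If all 200 planned patients were evaluable, each such patient would be worth 1/200 = 0.5 percentage points. A patient with a missed early event and a recorded later one is still counted in Table 52, but the early event is absent from Listing 53. The documents give no information on M.

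**3. Share of the window without planned collection** = g/(g + 12)
- g = 1: 1/13 = 7.7%
- g = 1.5: 1.5/13.5 = 11.1%
- g = 3: 3/15 = 20.0%

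Two features of the plan allow a larger share for some patients:
- The eligibility rule in SAP section 2.1 rounds the gap to whole months and resets enrollment to day 01. Taking the diagnosis day as 01 as well (an assumption, since diagnosis is held as month and year), a diagnosis dated 1 May with enrollment on 31 August passes: 92/30.4375 = 3.02, which rounds to 3. The actual span is 122 days, and 122/30.4375 = 4.0 months, so the share is 4/16 = 25%.
- Protocol 8.5 expects 20% to 40% drop-out. With g = 3, leaving at 6 months gives 3/9 = 33%.

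In the other direction, consent may precede the enrollment visit, which shortens the gap.

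**4. Illustration only.** Assume a constant hazard over the whole window, no capture before consent, and an assumed 12-month risk p. Then full-window risk = 1 − (1 − p)^(1 + g/12).
- g = 3: p = 10% gives 12.3%; 30% gives 36.0%; 50% gives 58.0%.
- g = 1.5: p = 10% gives 11.2%; 30% gives 33.1%; 50% gives 54.1%.

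Neither p nor the constant hazard comes from the documents. With no reportable event before consent, the shortfall is zero.

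**The case against.** **The count may not change.** If nothing was recorded before consent, a lower limit at diagnosis and one at consent select the same events over the same denominator, and Table 52 prints the same number. This stands as arithmetic. The number would still be labelled with a period that was not observed. If some early events were recorded, the SAP limit mixes them into the percentage, and the two limits can differ.

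**It cannot be said that nothing was captured.** The SAP was built on an eCRF version dated 30/11/2015, after the protocol, and that form is not among the documents. Protocol 10.2 sets a minimum and also asks investigators to keep records of all AEs. The Visit 1 schedule includes treatments and resource use related to adverse events. This stands: the documents support no *planned* AE collection before consent, and do not support that none occurred. Resource and treatment entries are not AE records with a start date, however, so they cannot feed a table that selects on AE start date.

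**The mandated set is narrow.** It covers ADRs, fatal AEs and pregnancies for one product. No enrolled patient can have died before consent, and a patient not on that product before consent adds no ADR to the mandated set. This stands, and it limits the size.

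**AE frequency is neither a primary nor a secondary objective, and the SAP starts other outputs at diagnosis too.** Both are true and both lower the weight of the point. The convention is harmless only where data were planned from diagnosis, as for resource use.

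**Conclusion.** The mismatch is in the text and its direction is certain: for the window named in Table 52, the reported percentage equals or understates the true one, and any early event that is entered is counted selectively. The size is unknown. For the mandated events it depends on how many patients took the sponsor's product before consent and had non-fatal ADRs then.

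Three stronger readings are tempting, and the documents do not support them:
- *That the AE frequency is understated by 11% to 20%.* Those figures are shares of calendar time at gaps of 1.5 and 3 months with 12 months of follow-up. They are not estimates of missed events, and 20% is not a maximum share for a patient either.
- *That AE incidence rates are diluted.* SAP 4.14 plans absolute and relative frequencies only. Protocol 8.7 says that events during follow-up will be described as incidence rates but sets no time origin, so a diagnosis-based denominator would have to be supplied by the reader.
- *That deaths before enrollment are lost.* Such patients are outside the denominator under either start date.

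What remains is a correction of the window and label of two safety outputs. It is modest in weight and worth making because it costs so little.

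**What to change.** In SAP sections 3 and 4.14, replace the lower limit by the date of informed consent, `[_PatientInfo.Date_CI]`. Retitle Table 52 and Listing 53 to run between informed consent and end of observation. List any event with an earlier onset separately, outside the percentage, and mark it as incompletely collected. If an AE incidence rate is produced under protocol 8.7, start person-time at consent.

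The consent date suits this purpose: SAP section 2.1 requires it to be non-missing and no later than the enrollment visit for every evaluable patient. It is a full date, whereas diagnosis is held as month and year, so the boundary also becomes sharper.

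Cost: SAP wording, one changed date comparison and one short additional listing. No new data.

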4 CONTENTS

The tables to be produced for interim report are in green (if analysis of follow up data is planned, data collected up to 3-month follow up will be considered).

Missing data will not be imputed and so patients with missing data will be excluded from the analyses of that variable(s).

If the investigator is unable to collect the requested information the data will be "NK" (Not Known) or "NA" (Not Available), if the investigator did not record the information the data will be "Not Recorded".

4.1 *Patient disposition*

Table 1. Enrolled and evaluable patients

The table will provide absolute and relative frequencies of:

- patients enrolled in the FIBRONET study
- patients evaluable at enrollment (as described in par. 2.1)
- patients who performed V2 (3 ± 1.5 months)
- patients who performed V3 (6 ± 1.5 months)
- patients who performed V4 (9 ± 1.5 months)
- patients who performed V5 (12 ± 1.5 months)

The percentages will be computed over the total number of enrolled patients.

Table 2. Reasons for non-eligibility to analyses

The table will describe the reasons for patient non-eligibility at enrollment.

Absolute and relative frequency distribution will be performed; the percentages will be computed out of the total number of enrolled patients.

Table 3. Premature study termination

The table will describe the distribution of patients withdrawn from the study ("Did the patient complete the study?"

[\[F19_STUDY_COMPLETION.SC_1\]](#) = "No") and the reasons for premature study termination ("Cause of drop out" [\[F19_STUDY_COMPLETION.SC_2\]](#)).

Absolute and relative frequency distribution will be performed; as for withdrawal, percentages will be computed out of the total number of patients evaluable at enrollment.

As regards reasons of withdrawal, the percentages will be computed out of the total number of patients withdrawn from the study. A patient could withdraw from the study for more than one reason.

The distribution of patients withdrawn for other reasons will be also reported in a separate table ("If other cause, specify:" ≠ missing [\[F19_STUDY_COMPLETION.SC_3\]](#)), if other reason frequency will be >20%.

Table 4. Months between baseline and follow up visits

The table will provide main descriptive statistics (mean, median, standard deviation, quartiles, min, max) of time (months) between baseline and each follow up visit.

Patients who performed each follow up visit will be considered.

4.2 Socio-demographics and clinical characteristics at enrollment

Table 5. Socio-demographic characteristics at enrollment

The table will provide:

- Main descriptive statistics (mean, median, standard deviation, quartiles, min, max) of patients' Age at enrollment ([\[_PatientInfo.Age\]](#))
- Patient distribution by Gender ([\[_PatientInfo.Gender\]](#))
- Patient distribution by Race ([\[F02_SOCIO_DEMOGRAPHICS.SD_Race\]](#))
- Patient distribution by Highest education level at baseline ([\[F02_SOCIO_DEMOGRAPHICS.SD_Education\]](#))
- Patient distribution by Employment status at baseline ([\[F02_SOCIO_DEMOGRAPHICS.SD_Employment\]](#))
-

Statistics will be computed out of the total number of patients evaluable at enrollment.

4.4 Primary objective: Clinical course of IPF during observation**Table 13. IPF symptoms**

The table will provide at enrollment and at V2, V3, V4, V5:

- Frequency distribution of patients with at least one IPF symptom [\[F06_IPF_SYMPTOMS.SYM_IPF_symptoms_YN\]](#)
- Frequency distribution of IPF symptoms [\[F06_IPF_SYMPTOMS.SYM_IPF_symptoms\]](#)

Descriptives will be computed out of the total number of patients who performed the specific visit.

Table 20. Lung Function Assessments – Spirometry at each study visit and variation during observation period

The table will provide at enrollment, V2, V3, V4, V5 main descriptive statistics (mean, median, standard deviation, quartiles, min, max) of:

- FEV1 (L) [\[F07_LUNG_FUNCTION_ASS.LU_FEV1\]](#)
- FEV1 of the predicted (%) [\[F07_LUNG_FUNCTION_ASS.LU_FEV1_predicted\]](#)
- FVC (L) [\[F07_LUNG_FUNCTION_ASS.LU_FVC\]](#)
- FVC of the predicted (%)
- FEV1/FVC (%) [\[F07_LUNG_FUNCTION_ASS.LU_FEV1_FVC\]](#)

- Total lung capacity (L) [\[F07_LUNG_FUNCTION_ASS.LU_TLC_Num\]](#)
- DLCO [\[F07_LUNG_FUNCTION_ASS.LU_DLCO_Num\]](#), along with the respective DLCO unit [\[F07_LUNG_FUNCTION_ASS.LU_DLCO_unit\]](#).
- DLCO of the predicted (%) [\[F07_LUNG_FUNCTION_ASS.LU_DLCO_Predicted_Num\]](#)
- SaO2 (%) [\[F07_LUNG_FUNCTION_ASS.LU_SAO2_Num\]](#)
- change at each follow-up visit vs baseline of FEV1 (L)
- change at each follow-up visit vs baseline of FEV1 of the predicted (%)
- change at each follow-up visit vs baseline of FVC (L)
- (absolute and relative) change at each follow-up visit vs baseline of FVC of the predicted (%)
- change at each follow-up visit vs baseline of FEV1/FVC (%)

- change at each follow-up visit vs baseline of Total lung capacity (L)
- change at each follow-up visit vs baseline of DLCO, along with the respective DLCO unit
- change at each follow-up visit vs baseline of DLCO of the predicted (%)
- change at each follow-up visit vs baseline of SaO2 (%)

Evaluable patients at the specific visit with spirometry performed [\[F07_LUNG_FUNCTION_ASS.LU_spirometry_YN\]](#) at study visit or in the previous 3 months will be considered.

Table 21. Lung Function Assessments – Emogas analysis at each study visit and variation during observation period

The table will provide at enrollment, V2, V3, V4, V5 the main descriptive statistics (mean, median, standard deviation, quartiles, min, max) of:

- PO2 (mmHg) [\[F07_LUNG_FUNCTION_ASS.LU_PO2_Num\]](#)
- PaO2 (mmHg) [\[F07_LUNG_FUNCTION_ASS.LU_PaO2_Num\]](#)
- PCO2 (mmHg) [\[F07_LUNG_FUNCTION_ASS.LU_PCO2_Num\]](#)
- PaCO2 (mmHg) [\[F07_LUNG_FUNCTION_ASS.LU_PaCO2_Num\]](#)
- change at each follow-up visit vs baseline vs PO2 (mmHg)
- change at each follow-up visit vs baseline vs PaO2 (mmHg)
- change at each follow-up visit vs baseline vs PCO2 (mmHg)
- change at each follow-up visit vs baseline vs PaCO2 (mmHg)

Evaluable patients at the specific visit with emogas analysis performed [\[F07_LUNG_FUNCTION_ASS.LU_emogas_YN\]](#) at study visit or in the previous 3 months will be considered.

Table 22. Lung Function Assessments – 6-minute walked distance test at each study visit and variation during observation period

The table will provide at enrollment, V2, V3, V4, V5 the main descriptive statistics (mean, median, standard deviation, quartiles, min, max) of:

- Start SpO2 (%) [\[F07_LUNG_FUNCTION_ASS.START_SPO2_Num\]](#)
- 6-minute walked distance (m) [\[F07_LUNG_FUNCTION_ASS.LU_6_minute_distance_Num\]](#)
- SpO2 at the end of the test (%) [\[F07_LUNG_FUNCTION_ASS.END_SpO2_Num\]](#)
- test duration [\[F07_LUNG_FUNCTION_ASS.LU_Time_stopped_Min, LU_Time_stopped_Sec\]](#). Minutest and seconds fields will be merged, and test duration will be expressed in minutes (seconds will be divided by 60).
- change in 6 minute walked distance test duration at each follow-up visit vs baseline. Minutes and seconds fields will be merged, and test duration will be expressed in minutes (seconds will be divided by 60).

The table will be provided overall and stratified by patients with test performed with O2 and without O2 [\[F07_LUNG_FUNCTION_ASS.LU_6_minute_test\]](#).

Evaluable patients at the specific visit with test performed [\[F07_LUNG_FUNCTION_ASS.LU_6_minute_YN\]](#) at study visit or in the previous 3 months will be considered.

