Dyspnea and cough are hallmark symptoms of IPF, and both appear to have important effects not only on quality of life (QoL) but also on survival [15]. IPF patients have unpredictable acute exacerbations, which could occur even with mild physiological impairment. At least half of hospitalizations are thought to be due to acute exacerbations of IPF [16]. Acute exacerbations of IPF are defined as an unexplained worsening or development of dyspnea. Their yearly incidence is between 10 and 15% of all patients. The prognosis of exacerbations is poor, with mortality ranging from 78% to 96% [22]. Other causes of exacerbations such as pulmonary embolism, congestive heart failure, pneumothorax, or infection need to be excluded.

Moreover, IPF patients experience depressive symptoms, which are correlated to QoL impairment and fatigue. QoL is further worsened as daily activities become restricted and patients grow increasingly oxygen dependent, debilitated, and dependent on others [15]. Not only prevalence of IPF is higher in men and in the older age groups, but also burden of disease [14]. In fact, higher increase in hospital admissions was found in men and older age groups by Navaratnam and colleagues [14]. They also estimated that the financial burden from IPF inpatient care alone in England is currently £16 million and will be almost £20 million by 2020.

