7.1 OBJECTIVES

Primary objective

1. In a sample of IPF diagnosed patients to describe the clinical course during 12 months of observation, in terms of:
 - symptoms
 - lung function (VC, FVC, FEV1, TLC, DLCO, pO₂, pCO₂; SaO₂, PaO₂ and PaCO₂ at rest)
 - exercise tolerance (6-minute walk distance test)

Secondary objective

1. Description of characteristics of IPF patients at enrollment in terms of:
 - key (socio-) demographic data
 - IPF risk factors, comorbidities
 - IPF disease severity and manifestation (including lung function, cardiopulmonary exercise testing and/or exercise capacity if available, laboratory values)
 - Methods used for IPF diagnosis
 - IPF treatment modalities (detailed information on prescribed drugs and dose; non-pharmacological treatment; lung transplantation)
2. To describe the frequency of exacerbations during 12 months of observation.
3. To describe HRQoL variation, measured with SGRQ, EuroQol (EQ) 5-dimension 5-level (EQ-5D-5L) descriptive system and EQ VAS, during 12 months of observation.
4. To describe health care sector-related costs from diagnosis up to the end of 12-month follow-up according to the Italian National Health Service (INHS) point of view.

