Table 1 two-sided 95% CI of expected frequency for IPF symptoms with sample sizes n=120 and 160. Cells are gray when the relative error - calculated as the ratio between 95% CI half-width and expected frequency - is lower than 30%.

Table 2 shows the two-sided 95% CI for expected mean of FVC, FEV1, DLCO and 6-min walked distance for sample sizes of n=120 (drop out=40%) and n=160 (drop out=20%), assuming the SD reported in the table and the confidence interval is based on the large sample z statistic [36]. IPF is a degenerative disease, therefore it is expected a worsening of symptoms, lung function and exercise tolerance. However, a conservative evaluation was performed by taking into account the two-sided 95% confidence interval.

| | Expected mean | SD | 95% CI | |
|--------------------------------------|---------------|-------|--------|--------|
| n=120 (drop out=40%) | | | | |
| FVC (L) | 2.37 | 0.73 | 2.24 | 2.50 |
| FEV1 (L) | 1.93 | 0.57 | 1.83 | 2.03 |
| DLCO (mL*min $^{-1}$ *mmHg $^{-1}$) | 9.19 | 3.92 | 8.49 | 9.89 |
| 6-min walked distance (m) | 372.9 | 82.63 | 358.12 | 387.68 |
| n=160 (drop out=20%) | | | | |
| FVC (L) | 2.37 | 0.73 | 2.26 | 2.48 |
| FEV1 (L) | 1.93 | 0.57 | 1.84 | 2.02 |
| DLCO (mL*min $^{-1}$ *mmHg $^{-1}$) | 9.19 | 3.92 | 8.58 | 9.80 |
| 6-min walked distance (m) | 372.9 | 82.63 | 360.1 | 385.70 |

Table 2 two-sided 95% CI of expected FVC, FEV1, DLCO and 6-min walked distance mean with sample sizes n=120 and 160. Cells are gray when the relative error - calculated as the ratio between 95% CI half-width and expected mean - is lower than 30%.

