8.7 DATA ANALYSIS

The statistical analysis will be performed on all evaluable patients who enter the study and meet the inclusion criteria. Patients with missing values will not be excluded from the analysis, their data will not be replaced; frequency of missing data will be given for all analyzed variables.

Descriptive analysis will be composed of means, medians, quantiles, proportions (with their respective 95% confidence intervals, CI) and contingency tables according to the nature of the variables. As a dispersion measurement the standard deviation and the interquartile range will be calculated. All events during follow-up will be described as incidence rates with 95% CI.

Statistical analysis will be performed using the SAS software.

The study objectives will be evaluated as follows:

Primary objective

To describe the clinical course of IPF during 12 months of observation

At each follow up visit the frequency of IPF symptoms (cough, fatigue, dizziness, chest pain, clubbing, bibasilar crackles) will be provided and the variation between visits will be described too mostly in terms of incident and worsening symptoms. Moreover, the score of the Modified Medical Research Council Dyspnea Scale for the evaluation of dyspnea at each follow up visit will be calculated together with the variation since baseline and between follow up visits.

The following outcomes will be also considered during the 12-month observation: lung function parameters (like VC, FVC, FEV1, TLC, DLCO, pO₂, pCO₂; SaO₂, PaO₂ and PaCO₂ at rest) and patient's exercise capacity (evaluated by means of 6-minute walked distance test, if available). The outcomes will be described at each follow up by means of descriptive statistics and the variation between visits will be provided too.

Secondary objectives

#1 Description of IPF patients at enrollment (socio-demographic data, IPF risk factors, comorbidities, disease severity and manifestation, methods for diagnosis, treatment modalities)

IPF patients enrolled at baseline will be described in terms of socio-demographic variables (e.g. age, gender, race, body mass index, educational degree, and employment status) and potential IPF risk factors (such as smoking habits, environmental exposure, drug exposure, other factors).

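### SAP Table 22 splits the walk test by oxygen use at each visit, so stratum means compare different patients over time and generally understate the decline

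*SAP*

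**What the plan says.** Exercise tolerance, measured by the 6-minute walk, is one of the three domains of the primary objective (Protocol 7.1). For the walk test and lung function, Protocol 8.7 undertakes that "the variation between visits will be provided too".

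SAP 4.4, Table 22, covers starting SpO2, walked distance, final SpO2 and test duration: "The table will provide at enrollment, V2, V3, V4, V5 the main descriptive statistics". Its population is set visit by visit: "Evaluable patients at the specific visit with test performed", at the visit or in the 3 months before it. On presentation: "The table will be provided overall and stratified by patients with test performed with O2 and without O2". The stratifying field, LU_6_minute_test, is on form F07, which also holds the walked distance recorded at each visit.

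The one change row listed is "change in 6 minute walked distance test duration at each follow-up visit vs baseline", expressed in minutes. SAP section 3 names the parameters for which change from baseline is computed, and walked distance is not among them.

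**The concern.** Oxygen status during the test can change over the year. The protocol expects decline: "IPF is a degenerative disease, therefore it is expected a worsening of symptoms, lung function and exercise tolerance". Its background adds, in general terms, that "patients grow increasingly oxygen dependent, debilitated, and dependent on others", and long-term oxygen therapy is recorded at all five visits.

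A patient who starts oxygen leaves one stratum and enters the other. If those who switch walk less far than the rest of the group without oxygen, that group's mean goes up when they leave. If they walk further than those already on oxygen, the other group's mean goes up when they arrive. Neither shift reflects any patient walking further.

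The table's title promises variation during observation. With no paired change in metres, comparing stratum means across visits is the only way the table offers to follow distance under like test conditions, and that comparison is the distorted one.

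**Working it through.** **1. The plan's own figure.** Protocol Table 2 assumes a mean of 372.9 m and SD of 82.63 m. The interval is mean ± 1.96 × SD/√n.
- n = 120: 1.96 × 82.63/√120 = 14.78, giving 358.12 to 387.68 m.
- n = 160: 1.96 × 82.63/√160 = 12.80, giving 360.10 to 385.70 m.

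Both match the protocol. They describe all patients together. The documents give no figure for either oxygen stratum, so everything below rests on assumptions.

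**2. Hand arithmetic (assumed groups, n = 160).** Take 112 patients never on O2 (mean 400 m), 24 who switch to O2 (330 m) and 24 always on O2. An overall mean of 372.9 m fixes the last group at (160 × 372.9 - 112 × 400 - 24 × 330)/24 = 289.3 m. At baseline the stratum without O2 averages (112 × 400 + 24 × 330)/136 = 387.6 m. If everyone loses d metres:
- without O2, change = (400 - d) - 387.6
- with O2, change = (289.3 + 330)/2 - d - 289.3

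| True loss d | Without O2 | With O2 |
|---|---|---|
| 5 m | +7.4 | +15.3 |
| 10 m | +2.4 | +10.3 |
| 20 m | -7.6 | +0.3 |
| 30 m | -17.6 | -9.7 |

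Strata fixed at baseline would show -d in every row.

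**3. Simulation with switching driven by walk distance.** Baseline ~ N(372.9, 82.63). Month 12 = baseline - d + N(0, 40). A test is on O2 if the distance falls below a threshold drawn afresh at each visit from N(T, 30), and nobody comes off O2. With d = 20 m:

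| T at baseline / month 12 | O2 share | Mean without O2 (m) | Mean with O2 (m) |
|---|---|---|---|
| 240 / 300 | 6.5% to 30% | 383.5 to 395.8 (+12) | 221.5 to 250.9 (+29) |
| 240 / 240 | 6.5% to 14% | 383.4 to 375.2 (-8) | 221.5 to 214.9 (-7) |
| 270 / 270 | 12% to 23% | 390.6 to 386.4 (-4) | 243.7 to 237.4 (-6) |
| 300 / 300 | 20% to 33% | 400.5 to 400.3 (0) | 264.9 to 258.7 (-6) |

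Strata fixed at baseline return -20 m each time. In the first row, patients still without O2 lost 12 m and those who switched lost about 44 m. With d = 40 m, the 240/300 rule still gives small to moderate rises (+2 and +22 m). All three constant thresholds give falls of 12 to 23 m in both strata, against a true 40 m. Loosening the link (240/300, threshold SD 100 m) with d = 20 m gives about +8 m without O2 and no change with O2.

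**4. Oxygen use only partly correlated with distance (correlation 0.3 to 0.7).** Both strata rise when the uniform loss is below about 4 to 10 m if 10 percentage points of patients move to O2, and below about 7 to 17 m if 20 points move.

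**5. Loss concentrated in switchers.** Others lose 5 m and switchers a further 40 m, with correlation 0.5 and O2 share going from 10% to 20%. The stratum without O2 shows +1.4 m and the stratum with O2 -10.2 m, against an overall -9.0 m. So one stratum can also slightly overstate the loss.

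**The case against.** - **The SAP does not say in words that the stratum follows the current visit.** True. It is an inference from the visit-level field and the visit-specific population. If another reading was meant, the table still needs a sentence saying so.
- **The overall rows are planned and are free of switching.** True, and they serve the primary objective directly. They mix tests with and without oxygen, however, so a reader wanting like-for-like conditions will turn to the strata.
- **The study is descriptive, and SAP Tables 45 to 48 show oxygen therapy at enrollment and at 3, 6 and 12 months.** A rise in oxygen use would be visible there, but not which walk tests changed condition.
- **Reversal needs a particular oxygen rule.** This stands. A reader might infer that Table 22 will show both strata improving while patients decline. In step 3 that depends on raising the threshold from 240 to 300 m, so that many patients switch without walking less far. With a constant threshold neither stratum rises at a 20 m loss. The documents give no oxygen shares or thresholds to support the stronger reading.
- **Strata fixed at baseline lose the separation by test condition.** Also true, so they should be added to the current split and not replace it.

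**Conclusion.** The point holds as a problem of interpretation confined to the stratified rows of Table 22. Read across visits, those rows compare different patients and generally understate the loss of walk distance. At a true loss of 20 m, the assumptions tried in step 3 with a threshold SD of 30 m give anything from both strata rising (about +12 and +29 m) to muted falls (0 to -8 m without O2, -6 to -7 m with O2). The understatement recurs across most of the assumptions. The reversal does not, and step 5 shows that understatement is not universal. All sizes depend on assumed oxygen shares, declines and links between oxygen and distance.

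The missing change in metres is a separate gap against Protocol 8.7, and it makes the distortion harder to see. The row for change in test duration may have been meant as change in distance. The conclusion rests on the rows as listed.

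**What to change.** In SAP Table 22:
1. State which visit's oxygen status defines the strata. Keep the overall rows and the current-visit split, and label the split as cross-sectional only.
2. Add paired change from baseline in walked distance (m) at V2 to V5: overall; by oxygen status at the baseline test, held fixed; and by transition group (no O2 at both tests, no O2 to O2, O2 at both). Show the transition groups together, because each is defined by what happened after baseline.
3. Report the number and percentage moving to oxygen at each visit. Add walked distance to the change variables in SAP section 3.

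The cost is SAP wording and a few more rows in one table, from data already collected. Cells will be small among switchers and in the baseline-oxygen group: at an assumed 6.5%, about 13 of 200 patients, or 8 to 10 of the 120 to 160 expected at month 12. Baseline-fixed strata will mix test conditions at follow-up, which the transition groups make visible.
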